9 STATISTICAL CONSIDERATIONS

9.1 POPULATIONS FOR ANALYSES

The following populations for analyses are defined:

Table 20 - Populations for analyses

Population	Description
Intent-to-treat (ITT)	
The intent-to-treat (ITT) population is the randomized population. All participants who have given their informed consent and for whom there is confirmation of successful allocation of a randomization number by the IRT will be included in this population. Participants will be analyzed according to the treatment group allocated by IRT, regardless of whether the participants received any study treatment or receive a different study treatment from that to which they were randomized.
 
This population will be used for the analysis of the co-primary efficacy endpoint.

Per Protocol-PK (PP-PK) population	
The Per Protocol PK population will include all randomized participants who have received at least eleven Isatuximab doses out of twelve up to C5D15 (one dose omission permitted during Cycle 1), with isatuximab C6D1 (predose) concentration results from PK sample collected within the defined per protocol time window and adequate documentation of dosing and sampling dates and times.
 
This population will be used for the analysis of the co-primary PK endpoint.

CT4W-PK population	
The CT4W-PK population for CT4W endpoint will include all randomized participants having completed administration of all the first 4 weekly isatuximab doses at Cycle 1, with isatuximab C2D1 (predose) concentration results from PK sample collected within the defined per protocol time window and adequate documentation of dosing and sampling dates and times.
 
This population will be used for the analysis of the CT4W PK endpoint.

Per Protocol population	
The PP is defined as all treated subjects who have measurable disease at baseline and have no major protocol deviations with respect to eligibility.
 
This population will be used for sensitivity analysis of ORR in the context of a non-inferiority design.

Safety	
The safety population will include ITT participants who have received at least 1 dose or a part of a dose of the study intervention. All analyses using this population will be based on the treatment actually received.
 
All safety analysis will be performed on this population.

Pharmacokinetic (PK)	
The PK population will include all participants with at least 1 available isatuximab concentration post-baseline (whatever the cycle and even if dosing is incomplete) with adequate documentation of dosing and sampling dates and times.
 
This population will be used for the analysis of PK secondary endpoints.

ADA	
The immunogenicity population will include all participants from safety population with at least 1 ADA result (negative, positive or inconclusive) post-baseline.

Screened participants are defined as any participants who signed the ICF.

Participants exposed to study intervention before or without being randomized will not be considered randomized and will not be included in any analysis population. The safety experience of these participants will be reported separately.

Randomized participants for whom it is unclear whether they took the study intervention will be considered as exposed and will be included in the safety population as randomized.

For any participant randomized more than once, only the data associated with the first randomization will be used in any analysis population. The safety experience associated with any later randomization will be reported separately.

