Co-Primary endpoint	ORR [stringent complete response (sCR), complete response (CR), very good partial response (VGPR), and partial response (PR)].	ITT	While not initiating new anti-cancer therapy Regardless of IMP discontinuation (treatment policy strategy).	This endpoint will be analyzed by calculating the relative risk between the SC and IV arm and its two-sided 95% CI using Farrington-Manning method and compare its lower CI limit with the pre-defined margin. In absence of confirmed PR or better, participants will be considered as non-responders, whatever the reason (including participants with missing or non-evaluable best overall response).
Co-primary endpoint	C_{trough} at steady state (corresponding to predose at C6D1).	PK-PP	(Principal Stratum strategy) Doses, administration scheme, sample collection, processing and result, time window of collection and adequate documentation.	The point estimate (ratio of geometric means for C_{trough} at steady state of SC/IV) together with its two-sided 90% CI will be calculated. The lower bound of the 90% CI will be compared with 80%. Participants who do not have all administrations up to C5D15 (one dose omission permitted at C1 only) and PK sample collected out of the prespecified time window are not included into the analysis population.

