The efficacy co-primary analysis will be conducted on the ITT population, defined as all participants who have given their informed consent and for whom there is confirmation of successful allocation of a randomization number by the IRT. Participants will be included in a treatment arm as randomized, regardless of whether participants receive any study drug or receive a different study drug from which they were randomized. The PK co-primary analysis will be conducted on the Per Protocol-PK (PP-PK) population defined as all randomized participants who have received at least eleven isatuximab doses out of twelve up to C5D15 (one dose omission permitted during Cycle 1), with isatuximab C6D1 (predose) concentration results from PK sample collected within the defined per protocol time window and adequate documentation of dosing and sampling dates and times.

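### The per-protocol set named for the ORR non-inferiority sensitivity analysis has no criterion for treatment received, so it cannot test dilution by wrong-route dosing (minor, cheap to close)

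*Protocol*

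**What the plan says.** Protocol Section 9.1, Table 20, defines the set in one sentence: all treated participants who have measurable disease at baseline and "have no major protocol deviations with respect to eligibility". Its purpose follows: "This population will be used for sensitivity analysis of ORR in the context of a non-inferiority design".

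The primary ORR analysis is ITT. Table 20 places participants in their allocated arm "regardless of whether the participants received any study treatment or receive a different study treatment from that to which they were randomized", and Section 4.1 says the same.

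Two other sets in Table 20 do carry dosing conditions. PP-PK requires "at least eleven Isatuximab doses out of twelve up to C5D15", and CT4W-PK requires all four weekly doses of Cycle 1.

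The ORR estimand in Section 3, Table 7, follows participants after they stop study drug but only while no new anti-cancer therapy has been started. On missing response it says: "In absence of confirmed PR or better, participants will be considered as non-responders, whatever the reason".

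Sections 9.2.2 and 9.2.5 do not mention the Per Protocol set, so nothing in the protocol widens it and no decision rule depends on it.

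**The concern.** In a superiority trial, ITT usually errs on the cautious side when some participants do not receive the assigned treatment. In a non-inferiority trial it can err the other way. If some of the SC arm is in fact treated by the IV route, their responses are IV responses, and the observed ratio moves toward 1 even when SC is worse. A per-protocol analysis is placed beside ITT largely to see whether the conclusion survives without those participants.

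As written, a participant randomised to SC but given IV, who was eligible and had measurable disease, is in both sets. Agreement between the two analyses would then say nothing about this kind of dilution, although a reader of the clinical study report might take it as reassurance on that point.

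**Working it through.** **Inputs.** From Section 9.5: 267 per arm, IV response rate 60.4%, true ratio 1.02 for power, margin 0.839, one-sided 2.5%, Farrington-Manning test. The protocol gives no wrong-route rate. I write it as x, the fraction of the SC arm treated as IV, and take 1% to 10% as an assumed range. Wrong-route participants are assumed to respond at the IV rate.

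**Step 1: reproduce the plan's power.** With p_IV = 0.604 and p_SC = 1.02 × 0.604 = 0.6161, the restricted estimates under p_SC = 0.839 p_IV are 0.5495 and 0.6550. The null standard error of p_SC − 0.839 p_IV is 0.0390, and the standard error under the alternative is 0.0389.

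Power = Φ[(0.1093 − 1.96 × 0.0390)/0.0389] = 80.0%. Exact enumeration of the two binomials gives 80.1%. The protocol states approximately 80%, so the test is set up as the plan intends.

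**Step 2: dilution under ITT.** Put SC exactly at the margin among those treated by the SC route: 0.839 × 60.4% = 50.7%. The ITT ratio is then 0.839 + x(1 − 0.839), and the error is the probability that the ORR test still concludes non-inferiority.

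| x | SC participants (267x) | ITT ratio | SC response rate | Error, normal approximation | Error, exact |
|---|---|---|---|---|---|
| 0% | 0 | 0.839 | 50.7% | 2.5% | 2.5% |
| 1% | 3 | 0.841 | 50.8% | 2.6% | 2.7% |
| 2% | 5 | 0.842 | 50.9% | 2.8% | 2.8% |
| 5% | 13 | 0.847 | 51.2% | 3.3% | 3.3% |
| 10% | 27 | 0.855 | 51.6% | 4.3% | 4.4% |

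For x = 5%, for example: (0.0049 − 1.96 × 0.0396)/0.0396 = −1.84, and Φ(−1.84) = 3.3%.

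**Step 3: the same participants in the Per Protocol set.** Suppose 2% of each arm is untreated (an assumption) and drops out of the set, which is analysed as randomised. Wrong-route participants then make up 5/98 = 5.1% of the SC arm instead of 5%, and the ratio is 0.839 + 0.051 × 0.161 = 0.847, as under ITT. At 10% the fraction is 10/98 = 10.2% and the ratio is 0.855, again as under ITT.

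A separate illustration puts the deviators in both arms, responding at 35.3% (the ORR without isatuximab in the earlier Phase 3 trial, Section 2.2.3.1). Deviation rates of 10% and 20% give errors of 3.5% and 4.8% in the Per Protocol set, against 3.5% and 4.7% in ITT. Removing the deviators returns the error to 2.5%, provided that their removal does not itself select on prognosis.

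**Step 4: not every deviation dilutes.** If a fraction f in each arm is counted as non-responders, the ratio is (1 − f) × 0.839 p_IV / [(1 − f) p_IV] = 0.839, and the error stays at 2.5%. The concern is therefore about participants who receive the other arm's treatment or who respond alike in both arms.

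**The case against.** **The assumed rates have little support in the protocol.** Allocation is by IRT. SC isatuximab is given by a health care professional with a dedicated injector used only in the SC arm, and administration is supervised. The guidance for reactions to SC dosing offers interruption, later resumption or discontinuation, not a change to IV. The ITT wording about receiving a different treatment is a rule for who is analysed, not a forecast of crossover. This stands, and it makes the 1% to 2% rows more plausible than the 5% to 10% rows.

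**Prohibited anti-myeloma therapy.** A reader might infer that participants who receive it dilute the comparison in the same way. Table 7 does not support that. Response counts only until new therapy starts, and anyone without a confirmed response by then is a non-responder. Step 4 shows that equal non-response in the two arms leaves the ratio unchanged.

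**The set still has a use.** A reader might infer that it is worthless or must agree with ITT by construction. It does test robustness to untreated and ineligible participants. If baseline means Cycle 1 Day 1, it can also remove eligible participants who fell below measurability after screening (Section 10.11). Agreement with ITT is assured only for treatment deviations.

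**The analysis plan could supply the detail.** Section 9.2 leaves technical detail to it, and it was not available for this review. A working list of deviations can properly sit there. The population, however, is fixed in the protocol and limited in terms to eligibility, so an analysis plan that added treatment criteria would depart from Table 20.

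**Conclusion.** The gap is real and small. The set named as the ORR sensitivity analysis for non-inferiority has no criterion for treatment received, so it cannot show whether wrong-route dosing influenced the ITT result. With SC at the margin, the one-sided ORR error is about 2.7% to 2.8% at the low wrong-route rates that the trial's procedures make more plausible, and 3.3% to 4.4% at 5% to 10%.

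These figures rest on an undocumented deviation rate confined to the SC arm, on wrong-route participants responding as IV participants do, and on the Per Protocol set being analysed as randomised, which Table 20 does not state.

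The figures should not be read as the chance of a false overall claim. Sections 9.2.2 and 9.2.5 require the PK co-primary to succeed as well, so they are upper bounds on that. The primary analysis is unaffected. This is a cheap improvement of minor severity.

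**What to change.** In Table 20, extend the Per Protocol definition to exclude pre-specified major treatment deviations likely to affect response, at least isatuximab not given by the randomised route. State that the set is analysed as randomised. Fix the list before database lock without reference to response. Keep ITT primary and report both analyses side by side.

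If the sponsor prefers not to add exclusions, describe the set as eligible and treated, and do not present it as the check on the non-inferiority conclusion.

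The cost is about one sentence in Table 20 and the deviation list. The downside is some post-randomisation selection and slightly fewer participants, which is acceptable in a supportive analysis. At the design ratio of 1.02, the set with 2% untreated removed (262 per arm) has about 79% power. Removing a further 10% of each arm as well would leave 235 per arm and about 75%. At wrong-route rates of 1% to 2% the further loss would be much smaller. The sample size does not change.

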9.2 STATISTICAL ANALYSES

The SAP will include a more technical and detailed description of the statistical analyses described in this section. This section is a summary of the planned statistical analyses of the most important endpoints including primary and secondary endpoints.

9.2.1 General considerations

Myeloma response and progression will be determined by Independent Review Committee based on central laboratory M-protein analysis and central radiology review using IMWG 2016 criteria.

The following stratification factors will be used:

- MM isotype (IgG versus non-IgG).
- Body weight (≤ 65 kg, > 65 to ≤ 85 kg, and > 85 kg).
- Number of prior lines (1-2 versus ≥ 3).

Primary and secondary endpoints will be analyzed by treatment arm.

Study treatment is defined as isatuximab (SC/IV) in combination with pomalidomide and dexamethasone. First dose of study treatment is defined as the first starting dose of any study intervention of isatuximab, pomalidomide or dexamethasone. Last dose of study treatment is defined as the last dose of any study intervention of isatuximab, pomalidomide, or dexamethasone.

For each of the safety parameters, the baseline will be defined as the last value or measurement taken up to the first dose of study treatment.

The observation period will be divided into 3 segments:

- The **pre-treatment** period is defined as the time the ICF is signed until the first dose of the study treatment administration.
- The **treatment-emergent (TE) period** is defined as the period from the first study treatment administration to the last study treatment administration +30 days.
- The **post-treatment period** is defined as the time starting 31 days after the last study treatment is administered to study closure or death, whichever comes first.

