1.3 SCHEDULE OF ACTIVITIES (SOA)

Table 1 - Schedule of activities

Evaluation/ Procedure ^a	Screening/Baseline	Cycle 1 ^{ee}			Cycle 2 ^{ee}		Subsequent cycles ^{ee}		End of treatment	Follow-up ^d	Notes	
	Days -28 to -1	D1 ^c	D8	D15 ^c	D22	D1 ^c	D15 ^c	D1 ^c	D15 ^c	D30 (±5) after last study treatment administration or before the next therapy		D = Day
Informed consents ^e	X											
Training participants on ePRO technology		X										
Contraceptive counseling ^f	X											
Inclusion/exclusion criteria	X											
Randomization ^b	X											
Hepatitis B and C and HIV serologies ^g	X										As clinically indicated	
Demography, medical/surgical and disease history ^h	X											
Performance status (ECOG)	X	X				X		X		X	ECOG = Eastern Cooperative Oncology Group	
Prior/concomitant medication	Continuously throughout the study period (and within 21 days before first IMP administration)											
Isatuximab administration and administration data		X	X	X	X	X	X	X	X			
Pomalidomide ⁱ		D1 to D21			D1 to D21		D1 to D21					

Evaluation/ Procedure ^a	Screening/Baseline	Cycle 1 ^{ee}				Cycle 2 ^{ee}		Subsequent cycles ^{ee}		End of treatment	Follow-up ^d	Notes
	Days -28 to -1	D1 ^c	D8	D15 ^c	D22	D1 ^c	D15 ^c	D1 ^c	D15 ^c	D30 (±5) after last study treatment administration or before the next therapy		D = Day
Dexamethasone (before isatuximab when co-administered) ⁱ		D1, 8, 15, and 22				D1, 8, 15, and 22		D1, 8, 15, and 22				
Patient expectations Questionnaire (PEQ) ^j		X										
Patient experience and satisfaction Questionnaire (PESQ) and Patient's assessment of treatment (PAT) Questionnaire ^k			X	X	X	X	X	on D1 of Cycles 3 and 4	C5 up to EOT	X		
HRUPQ questionnaire		X	X	X	X	X				X	X	
EORTC QLQ-C30 and QLQ-MY20, EQ-5D-5L Questionnaires		X				X				X	X	
IADL and ADL questionnaires		X										
Physical examination ^l	X	X				X		X			X	
Weight (height at baseline) ^m	X	X	X	X	X	X	X	X			X	
Vital signs (HR, Temperature, RR or SPO ₂ , BP) ⁿ	X	X	X									
Hematology ^o	X	X	X	X	X	X	X	X	up to C5	X		
Serum chemistry ^p	X	X	X	X		X		X		X		

Evaluation/ Procedure ^a	Screening/Baseline	Cycle 1 ^{ee}		Cycle 2 ^{ee}		Subsequent cycles ^{ee}		End of treatment	Follow-up ^d	Notes	
		Days -28 to -1	D1 ^c	D8	D15 ^c	D22	D1 ^c	D15 ^c	D1 ^c	D15 ^c	
PT/INR, PTT	X	As clinically indicated								X	PT/INR = prothrombin time/international normalized ratio PTT = partial thromboplastin time
Urinalysis ^g	X	As clinically indicated								X	

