4.5 DURATION OF STUDY PARTICIPATION

The participant will be considered in the study from informed consent signature until death, consent withdrawal, or the overall survival (OS) analysis cut-off date (approximately 30 months after LPI), whichever comes first.

The duration of the study for a participant will include a period for screening of up to 28 days. A cycle duration is 28 days. All AEs occurring after informed consent signature will be reported up to 30 days after last study treatment administration.

After study treatment discontinuation, participants will return to the study site 30 days after the last dose of study treatment for end of treatment (EOT) or before further anti-myeloma therapy initiation, whichever comes first ([Section 7](#)).

Related AEs and all SAEs regardless of relationship to the study treatment ongoing at the time of study treatment discontinuation will be followed during the follow-up period until resolution or stabilization. During the follow-up period, all (serious or non-serious) new AEs related to study treatment and any second primary malignancy will be collected and followed up until resolution or stabilization.

Participants who discontinue the study treatment due to PD will be followed up every 3 months (12 weeks \pm 7 days after last study treatment administration) for further anti-myeloma therapies, second primary malignancies, PFS2, and survival, until death or the final OS analysis cut-off date, whichever comes first. Participants who discontinue the study treatment prior to documentation of PD will be followed-up every 4 weeks until disease progression (even for participants who would initiate further anti-myeloma therapy without PD), and then after confirmation of disease progression, every 3 months (12 weeks) for further anti-myeloma therapies, second primary malignancies, PFS2, and survival, until death or the final OS analysis cut-off date, whichever comes first.

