8.4.3 Electrocardiograms

A 12-lead electrocardiogram (ECG) will be obtained as outlined in the SoA ([Section 1.3](#)).

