The PCSA criteria will determine which patients had at least 1 PCSA during the treatment period, taking into account all evaluations performed during the treatment-emergent period, including nonscheduled or repeated evaluations. The incidence of PCSA any time during the on-treatment period will be summarized by treatment group irrespective of the baseline level. For blood pressure/heart rate parameters, the incidence of PCSAs prior to study treatment administration at any cycle during the on-treatment period will be summarized by treatment group whatever the baseline level and/or according to the following baseline categories:

- Normal/missing.
- Abnormal according to PCSA criterion or criteria

The incidence of PCSAs during and after isatuximab administration at any cycle during the treatment period in the SC arm will also be summarized.

For laboratory variables graded by NCI-CTCAE. The number (and percentage) of participants with abnormal laboratory tests at baseline will be presented by grade.

The number (and percentage) of participants with abnormal laboratory tests during the treatment-emergent period will be summarized by grade. When appropriate, the number (and percentage) of participants with abnormality of any grade and with Grade 3-4 abnormalities will be provided.

For ECG, the incidence of participants with at least one abnormal ECG during the treatment-emergent period will be summarized regardless of the baseline level and according to the following baseline status categories:

- Normal/missing.
- Abnormal.

9.2.6.3 *Product complaints*

Product complaints will be summarized in the safety population.

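### In-window end-of-treatment ECG and laboratory results from Days 31 to 35 fall outside the treatment-emergent incidence tables, because that period stops at last dose +30 days

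*Protocol*

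**What the plan says.** **Analysis periods (Section 9.2.1).** The treatment-emergent period "is defined as the period from the first study treatment administration to the last study treatment administration +30 days". Anything later belongs to a separate post-treatment segment, which "is defined as the time starting 31 days after the last study treatment is administered to study closure or death". The last dose is the last dose of any of isatuximab, pomalidomide or dexamethasone. Table 6 defines the treatment period in the TEAE endpoint the same way, up to 30 days after the last dose.

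**EOT visit.** The EOT column of the Schedule of Activities (Section 1.3, Table 1) is headed "D30 (±5) after last study treatment administration or before the next therapy". Section 4.5 gives no window: "participants will return to the study site 30 days after the last dose of study treatment for end of treatment (EOT"). The visit is earlier if a new myeloma treatment starts sooner.

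**ECG schedule.** Section 8.4.3 only points to the schedule: "A 12-lead electrocardiogram (ECG) will be obtained as outlined in the SoA". The ECG row there shows a mark at screening, testing as clinically indicated, and one later mark.

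**Tables (Section 9.2.6.2).** "For ECG, the incidence of participants with at least one abnormal ECG during the treatment-emergent period will be summarized regardless of the baseline level". PCSAs are counted "taking into account all evaluations performed during the treatment-emergent period, including nonscheduled or repeated evaluations". Graded laboratory abnormalities are likewise summarised over the treatment or treatment-emergent period. The lead-in to that section says the analyses apply at each planned visit on the safety population.

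**AEs (Section 9.2.6.1).** AEs and deaths have their own post-treatment category. Laboratory and ECG results have no such category.

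**The concern.** The visit window and the analysis period both count from the last study treatment, but the window runs five days past the end of the period. A site can follow the schedule exactly and still produce an EOT result that the incidence tables do not count.

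For tests repeated every cycle this costs little. ECG is different: if the later mark in its row is the EOT visit, a participant seen on Days 31 to 35 contributes no routine post-baseline ECG to the ECG incidence table. Only ECGs prompted by a clinical reason remain for that participant. Whether a routine ECG counts would then depend on the day on which the visit was booked. Reason for stopping could also play a part, because participants who move quickly to another therapy have their EOT visit earlier, inside the period.

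**Working it through.** The protocol states no figure to reproduce. The check is a count of calendar days, with Day 0 as the last dose of any study drug.

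**Inputs**
- End of treatment-emergent period: Day 30 (Section 9.2.1).
- Start of post-treatment period: Day 31 (Section 9.2.1).
- EOT window: 30 − 5 = Day 25 to 30 + 5 = Day 35 (Section 1.3, Table 1).

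**Count**
- Days in the window: 35 − 25 + 1 = 11.
- Days inside the treatment-emergent period (25 to 30): 6.
- Days outside it (31 to 35): 5, and 5/11 = 45% of the nominal window.
- If the cut-off for these data ran to Day 35: 0 of 11 days outside.

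**Share of visits.** The protocol does not say how visits spread over the window, so the following are assumptions. For scatter around Day 30, each day d from 25 to 35 is weighted by w(d) = exp(−½((d − 30)/s)²). The share outside is the sum of w over Days 31 to 35 divided by the sum of w over Days 25 to 35.

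| Assumed timing | Share of EOT visits on Days 31 to 35 |
|---|---|
| All by Day 30 | 0% |
| Scatter around Day 30, s = 1 day | 30% |
| Scatter around Day 30, s = 2 days | 40% |
| Scatter around Day 30, s = 3 days | 43% |
| Even spread over Days 25 to 35 | 45% |

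All rows except the first ignore the clause that brings the visit forward when a next therapy starts. That clause moves visits earlier, so it lowers these shares.

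**Which results are affected**
- *ECG:* EOT appears to be the only routine assessment after screening, so an EOT visit on Days 31 to 35 removes the participant's routine ECG from the incidence table. Unscheduled ECGs on treatment still count.
- *Haematology and chemistry:* measured at least once per cycle on treatment. Losing one late value changes a worst-grade or PCSA count only if the abnormality, or its worst grade, is first seen at that visit.
- *AEs:* not lost. Onset from Day 31 goes to the post-treatment category, and the 30-day boundary matches the reporting period for all AEs in the schedule footnotes.

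**The case against.** **This is SAP detail.** Section 9.2 calls itself a summary and leaves technical description to the SAP, which is not at hand; visit windows normally belong there. That would settle the matter if the protocol were silent. It is not: it fixes the Day 30/31 boundary and names the treatment-emergent period as the scope of the tables. A SAP that follows this literally excludes the results, and one that includes them departs from Section 9.2.1.

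**The results are not lost.** The planned-visit lead-in in Section 9.2.6.2 leaves room for by-visit EOT summaries, and a clinically significant abnormality would also meet the AE definition. This stands. A reader might infer that the values disappear from safety reporting altogether, and the documents do not support that. But by-visit summaries do not put the values back into the period-limited incidence tables.

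**The size is uncertain.** A reader might take 5/11 to mean that about 45% of scheduled ECGs are excluded. That needs an even spread of visits and ignores the next-therapy clause. Only the day count is fixed by the documents.

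**The schedule matters more than the cut-off.** The primary cut-off is about 6 months after the last patient in, and median treatment duration on the IV combination in ICARIA-MM was 41 weeks (Section 2.2.3.1). Many participants may have no EOT visit at that analysis and so no EOT ECG under either rule. This also stands; the fix helps only participants who have had an EOT visit.

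**The extension to other tests is inferred.** PT/INR, PTT and urinalysis seem to follow the ECG pattern, so one might infer distorted coagulation and urinalysis tables. Section 9.2.6.2 names no such tables. The ECG row is itself broken in the text read, and no footnote confirms EOT for it.

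**Little depends on it.** ECG is not a listed endpoint, and the rule is the same in both arms. True, and it limits the weight of the point.

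**Conclusion.** The mismatch is real and follows from the protocol's own definitions: a compliant EOT visit on Days 31 to 35 yields laboratory and ECG results that the period-limited incidence tables of Section 9.2.6.2 do not count. Five of the 11 nominal window days are affected. The share of visits is unknown.

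The consequence is minor and mainly concerns ECG, assuming that the later mark in the ECG row is the EOT visit. Haematology and chemistry lose little. AE reporting is unaffected. The rule is common to both arms, so the documents give no ground to infer a built-in bias between SC and IV, and no co-primary or key secondary endpoint is involved. It is still worth correcting, because the stated rule misfires and the repair is small.

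**What to change.** Add one sentence to Section 9.2.1, carried into the SAP: for laboratory, vital-sign and ECG analyses, results from the in-window EOT visit (up to Day 35 after the last dose and before any further anti-myeloma therapy) are assigned to the treatment-emergent period. Leave the 30-day rule for AEs unchanged.

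No new data or visit is needed. The change should be made before database lock so that it cannot look data-driven. The small downside is that the laboratory and ECG cut-off can differ from the AE cut-off by up to 5 days: an abnormality on Day 33 would be treatment-emergent in the ECG or laboratory table but post-treatment if reported as an AE. A footnote to the affected tables should say so.
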